2.5.2 Statistical hypothesis, model, and method of analysis

The proportion of the hematological response will be summarized using point estimates and 90% exact (Clopper-Pearson) confidence intervals.

2.5.3 Handling of missing values/censoring/discontinuations

All withdrawals will be included in analyses up to the time of withdrawal. The subjects who discontinued from the trial before Week 26 will be treated as non-responders in the primary analysis.

2.5.4 Supplementary analyses

The hematologic response will also be derived programmatically using laboratory results and transfusion records instead of the hematologic response reported by the investigators in the response assessment CRF. The derived response at week 26 will be summarized and listed.

2.5.5 Supportive analyses

Subjects can respond according to one or more of three criteria: platelets (platelet counts and/or platelet transfusions), red cells (hemoglobin level and/or RBC transfusions), neutrophils (ANC counts). This results in 7 possible response combinations:

- Platelets
- Red Cells
- Neutrophils
- Platelets/Red Cells
- Platelets/Neutrophils
- Red Cells/Neutrophils
- Platelets/Red Cells/Neutrophils

The number and percentage will be made of the number of subjects who respond according to each combination of criteria at the Week 26 visit.

The number and percentage of assessment item for the detailed hematological response criteria will be presented as follows. In this summary, subjects could be counted as a response according to more than one criteria.

- Platelet Counts in platelet transfusion independent subjects
- Platelet Transfusion in platelet transfusion dependent subjects
- Hemoglobin Level in RBC transfusion independent subjects with baseline hemoglobin level < 90 g/L
- RBC Transfusion in RBC transfusion dependent subjects
- ANC counts

The primary efficacy endpoint will be summarized by the above subgroups listed in [section 2.2.1](#) for efficacy. The proportion of the hematological response in each subgroup will be summarized using point estimates and 90% exact (Clopper-Pearson) confidence intervals if applicable.

In addition, hematological responses will be listed.

The analysis for primary efficacy endpoint will not be reproduced at updated analysis and final analysis.

2.6 Analysis of the key secondary objective

Not applicable

2.7 Analysis of secondary efficacy objective(s)

The secondary efficacy objectives are to:

- To evaluate the efficacy of eltrombopag treatment at week 13 and week 52
- To evaluate the effect of eltrombopag on individual hematologic response (changes in neutrophil, platelet, hemoglobin)
- To evaluate the time to hematologic response and duration
- To evaluate the frequency and volume of transfusion (platelet and RBC)

2.7.1 Secondary endpoints

The following analyses Changes in platelet count, hemoglobin and neutrophil count, Duration of hematological response, Maximum duration of Platelet and RBC transfusion independence will be generated for the final CSR.

Hematological Response at Week 13 and Week 52

Hematologic response rate at Week 13 and Week 52 will also be assessed by investigator according to the International Working Group (IWG) criteria for the primary endpoints shown in the [Table 2-2](#) above.

The analysis for hematologic response rate at Week 13 will only be produced at primary analysis, and hematologic response rate at week 52 will only be produced at updated analysis.

Changes in platelet count, hemoglobin and neutrophil count

Value and changes in platelet count (in the absence of platelet transfusion), hemoglobin (in the absence of RBC transfusion) and neutrophil count (in the absence of G-CSF) will be calculated according to the lab test results entered into CRF.

Time to hematological response

Time to hematological response is defined as the time from the date of first study drug administration to the first hematological response which is defined in [Section 2.5.1](#). All subjects in the FAS will be included in the time to hematological response calculations.

These will be analyzed and plotted for four assessment criteria: Hematological Response; Platelet/Platelet Transfusion; Hemoglobin/RBC Transfusion; Neutrophils.

The analysis for time to hematological response will only be produced at primary analysis.

Duration of hematological response

For subjects who responded, duration of hematological response will be defined as the number of months from the first date of a hematological response which is defined in [Section 2.5.1](#) until the first date of a relapse (defined as not meeting the response criteria) or a death. Only subjects with at least 2 response assessments are included in the duration of response assessment. Patient still responding at the cut-off date will be censored at date of last response assessment.

These will be analyzed and plotted for four assessment criteria: Hematological Response; Platelet/Platelet Transfusion; Hemoglobin/RBC Transfusion; Neutrophils.

Frequency and amount of transfusion

For subjects receiving platelet transfusion at baseline, the frequency and the amount of platelets transfusion in each period (Baseline: 4 weeks before Day 1; Week 13, 26, 52: 4 weeks before each visit day) will be summarized. The same analysis applies to RBC transfusion (period will be extended to 8 weeks). The amount of transfusion will be defined as the sum of transfusion multiplied by the volume of transfusion.

The analysis for frequency and amount of transfusion will not be reproduced for final CSR.

Proportion of subjects with transfusion decrease

Subjects with platelet transfusion decrease is defined as subjects with transfusion decrease or transfusion free in each period (Week 13, 26, 52: 4 weeks before each visit day) compared to baseline (Baseline: 4 weeks before Day 1). 50% platelet transfusion reduction is defined as subjects with transfusion decrease of amount (units) at least 50% compared to baseline. The same analysis applies to RBC transfusion (period will be extended to 8 weeks). This analysis will be performed for the subgroup of subjects with baseline transfusion dependent.

The analysis for proportion of subjects with transfusion decrease will not be reproduced for final CSR.

Maximum duration of Platelet and RBC transfusion independence

Transfusion independence duration will be defined as the period from the next day of transfusion to the day before the next transfusion. Maximum duration of platelet and RBC transfusion independence for each subject will be picked for analysis.

Post-baseline transfusion independence will be achieved if subjects who are transfusion dependent at baseline become transfusion free for a period of at least 28 (platelets) or 56 days (RBCs). The time period for assessment of transfusion independence will be at any time during the treatment period. Baseline platelet and RBC transfusion dependence is defined as subjects receiving at least one platelet or RBC transfusion in the 4 weeks and 8 weeks, respectively, prior to the first dose of eltrombopag.

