## 5 Population

In this study, 20 adult patients previously diagnosed with SAA who have insufficient response following at least one course of IST in the period time of  $> 6$  months from the last course of IST will be enrolled (Note: As per local practice, patients who are eligible for HSCT will not be recruited into this study). Patients with insufficient response to previous IST include below populations:

- Relapsed patients, defined as patients with SAA who had achieved a CR (CR defined as transfusion independence, normal hemoglobin concentration, neutrophil count  $> 1.5 \times 10^9/L$ , and platelet count  $> 100 \times 10^9/L$ ) or PR (PR defined as transfusion independence and blood counts that do not meet criteria SAA but are not sufficient for a CR) after the last course of IST but have subsequently lost hematologic response and become transfusion dependent.
- Refractory patients, defined as any patient with SAA who has never achieved a PR or better following previous courses of IST or patient who has not achieved a PR or better following the initiation of the last course of IST .
- Patients with SAA who had achieved PR after the last course of IST with platelet count  $\leq 30 \times 10^9/L$ .

\*For relapsed patients, platelet count should  $\leq 30 \times 10^9/L$  at screening visit.

The investigator or designee must ensure that only patients who meet all the following inclusion and none of the exclusion criteria are offered treatment in the study.

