### 5.1 Inclusion criteria

Subjects eligible for inclusion in this study must meet **all** of the following criteria:

1. Chinese patients aged greater than or equal to 18 years old.
2. Patient with a previous diagnosis of severe aplastic anemia and had insufficient response following at least one treatment course in the period time of  $> 6$  months of immunosuppression with a regimen containing anti-thymocyte globulin (ATG), anti-lymphocyte globulin (ALG), and/or cyclophosphamide, or alemtuzumab.

Patient had severe aplastic anemia at diagnosis characterized by

([Red Blood Cell Disease \(Anemia\) 2017](#)):

1. Bone marrow cellularity  $< 25\%$ , or 25–50% with  $< 30\%$  residual haemopoietic cells and
2. At least two of the following (peripheral blood):
  1. Absolute neutrophil count  $< 0.5 \times 10^9/L$
  2. Platelet count  $< 20 \times 10^9/L$

3. Absolute reticulocyte count  $< 20 \times 10^9 / L$
3. Platelet count  $\leq 30 \times 10^9 / L$  at screening.
4. Patient must not currently have the option of stem cell transplantation, either because they are not a candidate, or because a suitable donor is not available.
5. Patient has an Eastern Cooperative Oncology Group (ECOG) performance status 0-2.
6. Patient with QTcF at screening  $< 450$  msec, or  $< 480$  msec with bundle branch block, as determined via the mean of a triplicate ECG and assessed at site.
7. Signed informed consent must be obtained prior to participation in the study.

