2.5.1 Primary endpoint

The primary endpoint is the hematologic response rate at Week 26, which is defined as the proportion of all subjects who meet any of the International Working Group (IWG) criteria at Week 26 shown in the table below. The primary endpoint will be based on the investigator assessment of response.

The analysis for primary endpoint as well as related supplementary and supportive analysis will not be reproduced for final CSR.

The primary analysis will be based on FAS and will include all data observed up-to the cut-off date.

Table 2-2 IWG criteria for Primary Endpoint

Assessment Item	Baseline transfusion status	Response Criteria
Platelet count	Platelet transfusion independent	Transfusion independent ⁽¹⁾ and increase from baseline by $20 \times 10^9/L$ or more
	Platelet transfusion dependent	No platelet transfusion requirement for 8 weeks
Hemoglobin	RBC transfusion independent	When the baseline hemoglobin level is < 90 g/L: transfusion independent and increase from baseline by 15 g/L or more
	RBC transfusion dependent	A decrease of at least 4 units in RBC transfusions in the post-treatment 8-week period (1 unit = RBC derived from 200 mL blood) Or no RBC transfusion requirement for 8 weeks (less than 4 units RBC in 8-week period at Baseline)

Assessment Item	Baseline transfusion status	Response Criteria
Neutrophil count	NA	(In the absence of G-CSF taken within 21 days preceding the blood sample collection) Increase from baseline by $0.5 \times 10^9/L$ or more, or (if $< 0.5 \times 10^9/L$ at baseline) increase by 100% or more

Note: No platelet/RBC transfusion requirement for 8 weeks means there is no any platelet/RBC transfusion received by patients during (Visit date-56 days) until Visit date. This definition also applies to Week 13 and Week 52.

(1) Transfusion independent means subjects did not receive platelet transfusion in the 4 weeks before Visit date.

During regular hematologic assessment, the exclusion period of transfusion and G-CSF are detailed below:

Platelet transfusion: 7 days preceding the assessment of platelet count

RBC transfusion: 14 days preceding the assessment of hemoglobin

G-CSF: 21 days preceding the assessment of neutrophil count

Definition of baseline Platelet Transfusion Independence/Dependence and platelet count

Baseline platelet transfusion independence/dependence and platelet count are defined as:

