2.7.2 Statistical hypothesis, model, and method of analysis

Hematological Response at Week 13 and Week 52

The number and percentage of subjects who meet the hematological response criteria (at Week 13 and Week 52 respectively) will be presented and exact 90% confidence interval will be reported. And the number and percentage of assessment item for the hematological response criteria and for the detailed hematological response criteria will be presented.

The derived response by programming at week 13 and Week 52 will also be summarized as above.

Changes in platelet count, hemoglobin and neutrophil count

Values and changes in platelet count (in the absence of platelet transfusion), hemoglobin (in the absence of RBC transfusion) and neutrophil count (in the absence of G-CSF) will be summarized at each visit. Descriptive statistics including mean, SD, median, 25th and 75th percentiles, minimum, and maximum will be summarized for the changes.

Median and interquartile range will be plotted.

Time to hematological response

The distribution function of time to hematologic response will be estimated using the Kaplan-Meier method and will be plotted. The median time to hematologic response along with 90% CIs will be presented. If a subject does not meet hematological response before or at the cutoff date, censoring will be performed using the date of the last assessment.

Duration of hematological response

The distribution function of duration of hematologic response will be estimated using the Kaplan-Meier method and will be plotted. If the number of relapses or deaths allows, the median time to hematologic response along with 90% CIs will be presented.

Relapse-free probability will be estimated using the Kaplan-Meier method at 3 months, 6 months, 9 monthes, one year, and yearly after as well.

Frequency and amount of transfusion

The frequency and the amount of platelets transfusion in each period (Baseline: 4 weeks before Day 1; Week 13, 26, 52: 4 weeks before each visit day) will be summarized by descriptive statistics including mean, SD, median, 25th and 75th percentiles, minimum, and maximum.

Proportion of subjects with transfusion decrease

The number and percentage of subjects with platelet or RBC transfusion decrease or transfusion-free in each period will be presented.

In addition, the number and percentage of subjects with 50% platelet or RBC transfusion reduction in each period will be presented.

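### The separate hemoglobin/RBC time-to-response curve can include subjects who have no hemoglobin/RBC response criterion, which would lower the curve and could leave its median unreached

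*SAP*

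**What the plan says.** SAP 2.7.1, under time to hematological response, fixes the population: "All subjects in the FAS will be included in the time to hematological response calculations". It then extends the analysis by lineage: "These will be analyzed and plotted for four assessment criteria: Hematological Response; Platelet/Platelet Transfusion; Hemoglobin/RBC Transfusion; Neutrophils". SAP 2.7.2 commits to a Kaplan-Meier curve and a median with a 90% CI. For subjects without a response, "censoring will be performed using the date of the last assessment".

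The response criteria are in SAP Table 2-2 (section 2.5.1). For subjects who are RBC-transfusion independent at baseline, the only hemoglobin criterion is "When the baseline hemoglobin level is < 90 g/L: transfusion independent and increase from baseline by 15 g/L or more". RBC-dependent subjects qualify through "A decrease of at least 4 units in RBC transfusions in the post-treatment 8-week period" or, if they needed fewer than 4 units at baseline, through 8 weeks without RBC transfusion.

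SAP 2.5.5 has two Week 26 tables by lineage. The table of seven response combinations carries no baseline restriction. The detailed-criteria table does, and one of its rows is "Hemoglobin Level in RBC transfusion independent subjects with baseline hemoglobin level < 90 g/L".

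**The concern.** An RBC-independent subject with baseline hemoglobin of 90 g/L or more cannot have a hemoglobin/RBC response, whatever the drug does. Nothing in SAP 2.7.1, 2.7.2 or 2.7.3 takes such a subject out of the hemoglobin/RBC curve, so the subject counts as at risk until the last assessment.

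The all-FAS rule is sound for overall response, which is the only time-to-response curve that Protocol 12.5.1 describes. The difficulty arises when the SAP carries the rule over to a single lineage whose criterion does not apply to everyone. A low plateau, or a median that is not reached, could then partly reflect baseline hemoglobin and not lack of response, and the output would not tell the reader so.

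**Working it through.** **1. Can such subjects be enrolled?** The blood-count part of the SAA definition in Protocol 5.1 ("At least two of the following (peripheral blood") lists neutrophils, platelets and reticulocytes at diagnosis. The screening limit is on platelets. There is no hemoglobin ceiling. Protocol 5 also admits certain partial responders, with "PR defined as transfusion independence and blood counts that do not meet criteria SAA but are not sufficient for a CR". So RBC-independent subjects can enter, and nothing bars a hemoglobin of 90 g/L or more. The documents do not say how many there are.

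**2. Which curves are affected?** Table 2-2 gives every subject a platelet route (by baseline transfusion status) and a neutrophil route, and therefore an overall route. Only the hemoglobin/RBC curve has subjects with no route. Duration of response is restricted to responders and is unaffected.

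**3. The plan's own figures.** The only design figures are in SAP 3.1. Clopper-Pearson 90% limits for 8/20 come out at (21.7%, 60.6%), and the largest half-width is 19.8% (at 10/20). Both agree with the SAP. No figure is stated for the hemoglobin/RBC curve.

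**4. Effect on the plateau.** Inputs: n = 20; k subjects without a criterion (assumed range); r responders among the other 20 - k. With everyone who has no response followed past the last response:

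- FAS plateau = r/20
- plateau among subjects with a criterion = r/(20 - k)
- ratio = (20 - k)/20 = 1 - k/20

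The ratio is 0.90, 0.80 and 0.70 for k = 2, 4 and 6.

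**5. Effect on the median.** The FAS curve needs 10 responders, which is 10/18 = 55.6%, 10/16 = 62.5% or 10/14 = 71.4% of the subjects who can respond. The restricted curve needs 9, 8 or 7, which is 50% each time. Example away from that boundary, k = 4 and r = 9: 9/16 = 56% (reached) against 9/20 = 45% (not reached).

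Binomial probability that the median is reached, by true rate among subjects who can respond (exactly half counted as reached):

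| k | 40%: FAS / restricted | 50%: FAS / restricted | 60%: FAS / restricted |
|---|---|---|---|
| 0 | 0.245 / 0.245 | 0.588 / 0.588 | 0.872 / 0.872 |
| 2 | 0.135 / 0.263 | 0.407 / 0.593 | 0.737 / 0.865 |
| 4 | 0.058 / 0.284 | 0.227 / 0.598 | 0.527 / 0.858 |
| 6 | 0.018 / 0.308 | 0.090 / 0.605 | 0.279 / 0.850 |

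**6. Does the SAP's censoring rule change this?** A simulation with last-assessment censoring, an assumed 60% response among those able to respond and 15% early exit among subjects without a response gave mean plateaus (FAS / restricted) of 0.565 / 0.625, 0.506 / 0.626 and 0.445 / 0.627 for k = 2, 4 and 6. The ratios are 0.904, 0.808 and 0.710, close to step 4.

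**The case against.** The case for leaving the plan alone has four parts.

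- **The number of such subjects is unknown.** This stands. A reader might infer that response in this lineage is understated as a fact. The documents show only that it can be.
- **The median may not be reached anyway.** This largely stands. The planning rate in SAP 3.1 is 40% for any lineage, or 8 of 20, and no lineage-specific rate is given. It is a Week 24 rate, so it is only a rough guide to a curve of first response at any time, but the example with 9 responders in one lineage lies above it. At 40% among those able to respond, the restricted curve reaches its median with probability of only 0.26 to 0.31 for k = 2 to 6. The denominator decides the matter only when that rate is at least 50% but below 50%/(1 - k/20).
- **The FAS curve is a legitimate description.** This stands. It gives the share of all treated subjects with a hemoglobin/RBC response by a given time. Time to response among those able to respond is a different quantity.
- **There is no contradiction inside the SAP.** A reader might infer that the curve conflicts with SAP 2.5.5. That goes too far. The curve is consistent with the unrestricted seven-combination table. It departs only from the split by baseline status in the detailed-criteria table, which forms no combined hemoglobin/RBC denominator. Those tables are also Week 26 rates, whereas the curve is time to first response.

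None of this removes the core point: the rule as written keeps subjects with no possible event in a lineage curve and does not call for their number to be shown.

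**Conclusion.** The point holds as a limited one about a single secondary, descriptive output. Under SAP 2.7.1 the hemoglobin/RBC curve can include RBC-independent subjects with baseline hemoglobin of 90 g/L or more. If it does, its plateau is lower than the rate among subjects who can respond by the fraction k/20: 10%, 20% or 30% for k = 2, 4 or 6. This rests on n = 20, complete follow-up and an assumed k. A median that is not reached cannot be put down to this rule without knowing k and the response rate. The primary endpoint and the overall, platelet and neutrophil curves are not affected.

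**What to change.** Present the hemoglobin/RBC time-to-response curve and median in subjects who are RBC-transfusion dependent at baseline, or RBC independent with baseline hemoglobin below 90 g/L. State the number excluded. Keep the FAS version of this lineage curve as a supplement, described as the share of all treated subjects. Leave the overall, platelet and neutrophil curves on the FAS. Record the change in SAP section 4, which at present reports none.

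The cost is a sentence in SAP 2.7.1, one filter on baseline variables that SAP 2.5.1 already defines, one extra output, and a slightly smaller n for that curve. SAP 2.7.1 produces time to response only at the primary analysis, so the restricted curve would be added to that analysis as a labelled output.

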#### **4.2.2 Rationale for duration of treatment**

In patients with refractory cytopenias due to severe aplastic anemia, there is little evidence for spontaneous recovery. In the extension period of study ETB115AUS28T, a total of 14 of 17 responders continued on eltrombopag in the extension arm, with a median time on drug of 12 months (range, 6-37 months). The majority of patients who remained on eltrombopag continued to show hematologic improvement, and 7 subjects eventually achieved trilineage responses.

In study ETB115AUS28T, responses only began to be observed beginning at the 3 month time point, and with continued exposure to drug, blood counts of all lineages improved towards the normal range gradually over time. Bone marrow cellularity began to normalize by 9-15 months.

Eltrombopag treatment will be continued in patients responding to the drug favorably beyond the primary endpoint at Week 26 until they reach blood count normalization sufficient for tapering or discontinuation of eltrombopag treatment. Toxicity and efficacy data will continue to be collected during that time to help identify the secondary endpoints of efficacy, duration of response and toxicities with extended duration of therapy.

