2.1.1 Data included in the analysis

The analysis cut-off date for the primary analysis of study data will be established after all enrolled patients have completed 26 weeks of treatment or have discontinued prior to Week 26. All statistical analyses will be performed using all data collected in the database up to the data cutoff date. All data with an assessment date or event start date (e.g. vital sign assessment date or start date of an adverse event) prior to or on the cut-off date will be included in the analysis. Any data collected beyond the cut-off date will not be included in the analysis and will not be used for any derivations.

All events with start date before or on the cut-off date and end date after the cut-off date will be reported as 'ongoing'. The same rule will be applied to events starting before or on the cut-off date and not having documented end date. This approach applies, in particular, to adverse event, concomitant medication reports and exposure to eltrombopag. For these events, the end date will not be imputed and therefore will not appear in the listings.

The analysis cutoff date for the updated analysis and final analysis of study data will be established after all patients have completed Week 52 or discontinued prior to Week 52 and at the end of the study respectively.

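### Time to response, including the three lineage curves, stops at the primary-analysis cut-off, so lineage responses first seen after that date enter no time-to-response result, although their duration is analysed for the final CSR

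*SAP*

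**What the plan says.** SAP 2.7.1 defines time to hematological response from first dose to first response in all FAS subjects and adds: "These will be analyzed and plotted for four assessment criteria: Hematological Response; Platelet/Platelet Transfusion; Hemoglobin/RBC Transfusion; Neutrophils". It then limits the whole analysis: "The analysis for time to hematological response will only be produced at primary analysis". Time to response is also absent from the list, at the head of the same section, of secondary analyses to be generated for the final CSR. Duration of hematological response, specified for the same four criteria, is on that list.

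SAP 2.1.1 fixes the data that count. The primary cut-off "will be established after all enrolled patients have completed 26 weeks of treatment or have discontinued prior to Week 26". Up to that date everything is used: "All statistical analyses will be performed using all data collected in the database up to the data cutoff date". After it nothing is: "Any data collected beyond the cut-off date will not be included in the analysis and will not be used for any derivations". Under SAP 2.7.2, for a subject without response at the cut-off, "censoring will be performed using the date of the last assessment".

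Protocol 12.5.1 defines the endpoint without tying it to the primary analysis. Protocol 9.2 says that the final CSR will analyse all data available up to the final cut-off. SAP section 4 reports no departure from the protocol's analyses. The SAP document history records that sentences limiting which analyses are repeated were added in the versions of 09-Feb-2022 and 22-Mar-2023, without naming time to response.

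**The concern.** Secondary objective 3 pairs time to response with its duration. Both start from the same event, the first date on which a criterion is met. The plan follows that event to the end of the study for duration but only to the primary cut-off for time to response.

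The gap falls on the lineage curves. A subject who responds in one lineage at Week 26 continues treatment and may first respond in a second or third lineage later. Protocol 4.2.2 leads one to expect this. In the earlier study, with continued exposure, "blood counts of all lineages improved towards the normal range gradually over time", and in its extension "7 subjects eventually achieved trilineage responses". A reader of the final CSR would see such a subject in the duration analysis for a lineage, while the only time-to-response curve for that lineage shows the same subject as censored.

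**Working it through.** No figure in the plan bears directly on this point. Its one precision figure, the exact 90% interval of 21.7% to 60.6% for 8 of 20, reproduces, but nothing here depends on it.

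**Which first responses are counted**

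| First response in a criterion | Time to response | Duration of response |
|---|---|---|
| Up to the subject's own Week 26 | Counted | Counted |
| After own Week 26, before the primary cut-off | Counted | Counted |
| After the primary cut-off | Never counted | Can be counted in the final CSR |

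Duration also requires at least two response assessments (SAP 2.7.1). The middle row matters: Week 26 is the minimum follow-up of subjects still in the study, not a ceiling.

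**How much follow-up lies beyond the cut-off**

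The documents do not give the accrual period, so it is assumed. With 20 evenly spaced entries over A weeks, no dropout, and a cut-off when the last subject reaches Week 26:

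follow-up at cut-off = 26 + (A − own entry week).

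A plausible upper value for A comes from the SAP version dates. From 06-Dec-2019 (before first visit) to 19-Aug-2021 (before primary lock) is 622 days, and 622/7 = 88.9 weeks. Subtracting 26 leaves 62.9, so A is taken up to 62. This treats the cut-off as no later than the second date.

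| A (weeks) | Followed beyond Week 26 | Reached Week 52 | Week 26–52 person-time before cut-off | After cut-off |
|---|---|---|---|---|
| 0 | 0 of 20 | 0 | 0% | 100% |
| 13 | 19 | 0 | 25% | 75% |
| 26 | 19 | 1 | 50% | 50% |
| 39 | 19 | 7 | 66% | 34% |
| 52 | 19 | 10 | 74% | 26% |
| 62 | 19 | 12 | 78% | 22% |

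Some follow-up is lost at every value of A in this range. If response is formally recorded only at Weeks 13, 26 and 52 (the efficacy visits in Protocol section 8 and the windows in SAP Table 2-1), a new lineage response would be dated near Week 52. Only the 0 to 12 subjects in the third column could then contribute one.

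**How many events are lost**

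At the planning rate, 0.40 × 20 = 8 subjects respond and continue. Those already responding in all three lineages have nothing left to gain. The number affected therefore lies between 0 and 8, which is every possible value and so not an estimate.

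**The case against.** The strongest reply has four parts.

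- **The protocol endpoint is time to any response.** That is the overall curve, and it can gain little later because Week 26 non-responders stop treatment (Protocol 3 and 6.1.5). The lineage curves are a SAP specification, which the document history dates to August 2021. This stands: the protocol-specified overall result is barely touched.
- **Kaplan-Meier handles right-censoring.** An earlier cut-off shortens a curve without making it wrong up to that point. This stands too, under the usual independent-censoring assumption.
- **Later lineage gains are visible elsewhere.** Week 52 response is tabulated by assessment item and detailed criterion, and changes in the three counts are repeated for the final CSR. This stands in part: a rate at a fixed visit, or a mean change, does not show when response began.
- **Which descriptive outputs to repeat is the sponsor's choice** in an estimation study of about 20 subjects, and the SAP states the choice openly. This is fair, but the choice breaks the pairing with duration, no reason is given, and section 4 does not list it.

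Two stronger readings are tempting, and the documents support neither. A reader might infer that any lineage response after Week 26 is lost. That would be true only if all subjects entered together, because the limit is a calendar date. A reader might also apply the earlier study's 7 trilineage responders among 17 to 8 responders here (8 × 7/17 = 3.3) and expect about three missing subjects. Protocol 4.2.2 does not give 17 as the denominator for the 7 (14 of the 17 continued in the extension) and does not say when each lineage first responded. Nor does it define trilineage response there. If the term carries the Protocol 4.2.1 meaning, it rests on absolute levels held for more than 8 weeks, not on the change-from-baseline and transfusion criteria used here.

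**Conclusion.** The point holds as a limited one. Lineage responses first seen after the primary-analysis cut-off enter no time-to-response result, while their duration can be reported in the final CSR. The protocol does not impose this limit, and the SAP does not declare it as a change.

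The primary endpoint is untouched, and the overall curve and all estimates up to the cut-off are little affected. The documents therefore do not support a claim that secondary objective 3 as a whole rests on truncated data. The loss is follow-up and events on the three lineage curves. Its share of Week 26 to 52 person-time depends entirely on the assumed accrual pattern, and the number of events lost cannot be derived without patient data.

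**What to change.** Replace the limiting sentence in SAP 2.7.1 with: *Time to hematological response, for all four criteria, is produced at the primary analysis and repeated at the final analysis with data up to the final cut-off. First-response dates are those used for duration of response. Subjects without a response in the criterion concerned are censored at their last assessment.* Add time to response to the list of final-CSR analyses at the head of the section.

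The final analysis is the right place. The current SAP version, dated 22-Mar-2023, precedes only the final database lock, and a re-run at Week 52 would leave later lineage responses with a duration but no time to response. Including the overall curve keeps all four on one cut-off. If the restriction is kept, SAP section 4 should list it with a reason.

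The programs exist and the first-response dates are already needed for duration, so the cost is a few more outputs. The repeated curves may differ from those in the primary CSR, so each must be labelled with its cut-off.
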